With the safety and efficacy of RES demonstrated in multiple clinical contexts, our study aims to ascertain if RES can be used for cosmetic purposes to enhance healing following CO2 partial field ablation. CO2 laser resurfacing is often used as an adjunct treatment during facelift procedures to address signs of aging in the periorbital and perioral areas. The laser treatment works by a superficial layer of the skin, requiring complete reepithelialization of laser treated areas. This process results in significant post-operative erythema, pain, and downtime for the patient. During the facelift procedure, excess skin is removed and discarded. In our proposed study, this excess skin would be repurposed via processing with the RECELL system to be used as a regenerative epidermal suspension graft on CO2 laser treated areas. The excess skin removed on a facelift is a greater surface area than the required 2 x 3 skin graft that is required for the common 80:1 expansion used in burn surgery. Therefore, we should have significant amounts of excess skin that could be repurposed as a split thickness skin graft that can be used for the recell. There will not be any additional skin removed further than what is required for the

facelift. We will use an 0.008 inch Weck blade to repurpose the excess skin into a split thickness skin graft need for the recell.

Device Output Characterization

We do not have any plans for this.

Objectives

The primary objective and study endpoint will be safety. The number of skin reactions will be evaluated to measure the primary endpoint over the treated area vs placebo control.

Methods and Measures

Design

Randomized, Double Blind, Placebo Controlled

Setting

Atrium Health Wake Forest Baptist Department of Plastic and Reconstructive Surgery

Subjects selection criteria

- **Inclusion Criteria**

- Adults 22 years or older

- Patients undergoing facelift with perioral CO2 laser treatment

- Skin that is Fitzpatrick Score 1 or 2

- Subjects who are in general good health

- Subjects who fully understand the research nature of this study and sign the informed consent

- **Exclusion Criteria**

- Prior perioral CO2 laser resurfacing

- Allergy to components of preparation system

- Subjects who have cosmetic or surgical treatment in perioral area within 3 months before the study (including laser, chemical peels, fillers, botulinum toxin).

- Subjects with existing open wounds on the face

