The perioral area of the face will be treated with CO2 laser. Laser setting will be determined by the treating surgeon for each individual patient. The laser is a Lumenis Ultrapulse/Surgitouch CO2 laser, 510(k) Number K030147. A laser (light amplification by stimulated emission of radiation) based device having coherence, collimated and typically monochromatic radiation. Typically indicated to cut, destroy, remove or coagulate tissue, generally soft tissue, for general surgical purpose in medical specialties of general and plastic surgery, dermatology/aesthetic, podiatry, otolaryngology (ent), gynecology, neurosurgery, orthopedics (soft tissue), dental and oral surgery, and dentistry. The classification regulation 21 cfr 878.4810 describes a device that is carbon dioxide or argon laser intended to cut, destroy, remove or coagulate tissue by the light. This laser is typically used in our practice for skin resurfacing to reduce the signs of aging, improve skin texture, laxity and tone, and reduce scars and stretch marks. Typical settings to be used for severe facial photoaging with Total FX is: Active FX, Energy (mj) 100-125, Scan Size 6-7 mm, Density 2-3, Hertz 100-200, Repeat Delay 0.3-1.5 seconds, number of passes 2. Deep FX, Energy (mj) 12.5-22.5, Scan Size 10 mm, Density 5-20%, Hertz 300-600, Repeat Delay 0.3-1.5 seconds, Number of Pulses 1-2, number of passes 1-2. The patient would be randomized and blinded to either left perioral or right perioral RECELL application. The surgeon would also be blinded to which side received RECELL treatment or Placebo (saline spray). Randomization would occur before study initiation with subjects assigned either left perioral or right perioral RECELL treatment based on their subject enrollment number. The study team member who prepares and blinds the RECELL will create the list of subject ID numbers with subject ID number randomly assigned to either left perioral or right perioral treatment group. This will be completed prior to any patient enrollment in the study. This spreadsheet will be password protected and only accessible to study coordinators and the team member responsible for preparing RECELL.

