RECELL® is a single-use, stand-alone, battery-operated, regenerative epidermal harvesting device containing enzymatic and delivery solutions, sterile surgical instruments, and actuators. The cell suspension contains a mixed population of cells, including keratinocytes, fibroblasts, and melanocytes, obtained from the disaggregation of the skin sample. The Enzyme used to process the cells is a biological agent and as such may have slight variations in color and texture. The enzyme is derived from animal tissue and has undergone filtration and terminal sterilization by gamma irradiation.

Intraoperatively, RECELL and Placebo will be provided to surgeons and assistants in opaque application devices prepared by a trained, designated study team member.

Both the treatment and placebo sides, will be dressed with a standard regenerative epidermal suspension post treatment dressing (Telfa Clear and Xeroform). Xeroform will be removed on postoperative day 1. Telfa clear will be removed on postoperative day 7. Patients will return to clinic for follow up at the following interval:

- Post Operation Day 1
- Post Operation Day 7
- Post Operation Day 14
- 1-month Post Operation
- 2-months Post Operation
- 3-months Post Operation

There is always a chance the patient may need to be withdrawn from the study. The main consideration for stopping is the dressings, as the Recell will already be sprayed. If the patient cannot tolerate the dressings, we will stop and remove them from the study. Otherwise, we will deal with complications similar to how we would deal with other laser reactions- local wound care, anti-virals, etc.

Any signs of anaphylactic events will lead to the study stopped immediately and unbinding. We will immediately wash the cell suspension off of the face with 3 liters of normal saline (NS) while treating the anaphylaxis per institutional protocol (including submuscular epinephrine).

Any high incidence of serious adverse events (any serious adverse event, including severe infection requiring return to the operating room) will warrant early unbinding and assessment of safety immediately.

Subjects will be able to withdraw from the study for any reason and at any time. We can remove the cell suspension with removal of dressings and 3 liters of NS wash.

Outcome Measure(s)

Preoperatively patient baselines will be established with standardized studio photographs, and photos using the Quantificare LifeViz® Camera, as well as in person evaluation.

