Intraoperatively, the patient will be photographed in CO2 treated areas with the Quantificare LifeViz® Camera and standardized photography. This camera measures lines, closing surfaces, volume, depth, and perimeter of the skin surface for microstructure analysis. We will analyze this data to track progress throughout the study.

Postoperatively, patients will be evaluated at each visit via in person evaluation by the surgeon, as well as using standardized photography, Quantificare LifeViz® Camera photos, administration of applicable FACE-Q scales (patient completed survey), and pain score (standard 1-10 pain scale). Please find FACE-Q scales in Appendices B-H.

Please find study calendar in Appendix A.

Analytical Plan

Results will be analyzed initially using descriptive statistics. Comparison between groups will be done using Fisher's exact tests for proportions, and t-tests or ANOVA procedures for continuous variables. Regression analysis will be performed to identify independent outcome predictors. Other inferential statistical analysis will be conducted as appropriate.

Human Subjects Protection

Collection of patient-identifying information will be limited to what is necessary to conduct analysis that is accurately linked to a given subject. Other than the master 'linkage' file, patient names, and medical record numbers will be removed and subjects will be associated with an abstracted unique Study ID. DOB will only be collected in order to dynamically calculate age at operative and follow up time points. Data will be stored electronically on the Wake Forest School of Medicine's secure REDCap server, a HIPAA-compliant web platform. Information for each subject will be entered directly from EPIC to the secure REDCap database, so data will not be stored on portable storage devices (including USB drives). In addition to study informed consent, photography consent will be obtained.

Subject Recruitment Methods

Patients who are scheduled to undergo elective facelift surgery with perioral CO2 laser resurfacing will be identified in the Plastic Surgery Clinics at both Janeway Tower and Vest Mill office locations. Any patient meeting inclusion criteria will be recruited during preoperative planning. Patients will have study information provided by a qualified study team member. There will be no compensation provided for this study, but the laser will be offered at no cost for participants.

Informed Consent

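### Each patient receives both RECELL and saline, but proportions are to be compared with Fisher's exact test, which assumes independent groups and cannot use the pairing

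*Combined protocol and SAP*

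**What the plan says.** Under Interventions and Interactions in the combined protocol and SAP, the random element is the side of the face: "The patient would be randomized and blinded to either left perioral or right perioral RECELL application". The other side receives saline spray, and "Both the treatment and placebo sides, will be dressed with a standard regenerative epidermal suspension post treatment dressing". The words split-face and matched pairs do not appear, but no other reading fits a treatment side and a placebo side on one patient.

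The Objectives section makes safety primary: "The number of skin reactions will be evaluated to measure the primary endpoint over the treated area vs placebo control". Sample Size gives 10 patients with no calculation.

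The Analytical Plan begins "Results will be analyzed initially using descriptive statistics", then commits to tests: "Comparison between groups will be done using Fisher's exact tests for proportions, and t-tests or ANOVA procedures for continuous variables". It closes with "Other inferential statistical analysis will be conducted as appropriate". No McNemar, paired t, signed-rank, mixed-model or other within-patient method is named anywhere.

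**The concern.** The design makes each patient their own control, while the named test for proportions treats the two sets of sides as two unrelated groups. Fisher's test sees only how many sides reacted in each condition. It cannot see whether the same patients reacted on both sides, which is the information that the design was built to supply.

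Safety is the primary endpoint and there are only 10 patients, so most of what can be learned lies in the within-patient difference and its interval. The plan names neither. For continuous side-level outcomes, an analyst who took the comparison between groups literally and ran an unpaired t-test would discard precision already paid for by the design.

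**Working it through.** **Inputs.** From the documents: 10 patients, one RECELL and one saline side each, and Fisher's test for proportions. The documents give no alpha, event rate, SD, effect size or within-patient correlation, so the sample size cannot be reproduced. Two-sided 0.05 and all rates and correlations below are assumptions. Ten pairs is the maximum; withdrawals would reduce it.

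**1. What Fisher ignores.** Suppose 5/10 RECELL sides and 2/10 placebo sides react. Three pairings with these margins are shown below (b = patients reacting on the RECELL side only, c = on the placebo side only).

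| b v c | phi | Fisher p | Independent-samples score CI | Paired (Tango) CI |
|---|---|---|---|---|
| 3 v 0 | 0.5 | 0.35 | -0.11 to 0.60 | -0.06 to 0.60 |
| 4 v 1 | 0 | 0.35 | -0.11 to 0.60 | -0.15 to 0.64 |
| 5 v 2 | -0.5 | 0.35 | -0.11 to 0.60 | -0.22 to 0.68 |

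The risk difference is 0.30 in every row. The independent-samples analysis cannot tell the three datasets apart; the paired interval can.

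**2. Direction of the error.** The true reaction rate is set to 0.3 on both sides and all paired tables are summed exactly. Fisher's actual two-sided size is 1.2% at correlation 0, 0.3% at 0.3 and 0.07% at 0.5. It is conservative, and more so as correlation rises.

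**3. Fisher against exact McNemar.** McNemar is a binomial test on b + c discordant patients. A 5 v 0 split gives 2 × 0.5^5 = 0.0625, and 6 v 0 gives 2 × 0.5^6 = 0.031. At least 6 discordant patients are therefore needed. Among all 10-pair tables with RECELL worse, the two tests disagree at 0.05 in six. Fisher is the significant one in all six, so McNemar can never have more power at this sample size. Four of the six have negative phi. In the other two phi is undefined (5/10 v 0/10 and 10/10 v 5/10), and each gives Fisher 0.033 against McNemar 0.0625. Power, Fisher v McNemar, at correlation 0.3:
- 40% v 10% reacting: 11% v 5.5%
- 50% v 10% reacting: 25% v 17%
- 70% v 20% reacting: 40% v 38%

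**4. Continuous side-level outcomes.** The variance of the mean difference is 2σ²(1 − ρ)/n when paired. The unpaired formula uses 2σ²/n. The unpaired standard error is too wide by 1/√(1 − ρ): 1.20 at ρ = 0.3, 1.41 at 0.5 and 2.24 at 0.8. Simulated power for a 0.8 SD difference with 10 pairs:

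| ρ | Unpaired t | Paired t |
|---|---|---|
| 0 | 39% | 36% |
| 0.3 | 38% | 48% |
| 0.5 | 37% | 62% |
| 0.7 | 35% | 83% |

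**5. Reaction counts per side.** Poisson counts with a shared gamma patient effect of variance v have correlation v√(m1·m2)/√((1 + v·m1)(1 + v·m2)). At means 0.2 v 0.4, v = 5 gives 5 × 0.283/√(2 × 3) = 0.58, and v = 11.67 gives 0.76. Coverage of a nominal 95% paired t interval is 83% and 70% respectively; an unpaired t interval covers 89% and 78%. At means 0.5 v 1 and correlation 0.76 the figures are 84% and 90%. The paired t interval is thus unsafe as the main result for infrequent, correlated counts. The Tango interval for any reaction per side covered at least 95% in every count setting simulated (means 0.2 v 0.4 up to 2 v 4).

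**The case against.** **The mismatch is narrow.** The primary endpoint is a number of reactions, Fisher is assigned only to proportions, and no per-side proportion is defined. The adverse events listed for reporting are not tied to a side, and FACE-Q and pain scores are not said to be scored by side. This stands as a limit: the point covers only outcomes recorded per side. It does not remove the point, because the primary comparison is explicitly treated area against placebo, and Fisher is the only test named for a proportion of sides reacting.

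**The plan leaves room.** t-tests and ANOVA have paired forms, so a reader who infers that those are wrong goes beyond the documents. The closing clause does not rescue Fisher: it admits other analyses in addition and does not replace the one named. Starting with descriptive statistics does not withdraw the tests either.

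**The paired test buys no power.** This is correct. A reader might infer that pairing would make an excess of reactions easier to detect, or that Fisher risks false alarms. Neither is supported: McNemar has no more power at n = 10, and Fisher is conservative under positive correlation. Nor is the switch free of consequence. At 5/10 v 0/10, a natural form for a safety signal, significance is lost. The case for proportions rests on validity and estimation, not on power.

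**The visits are undefined.** There are six postoperative visits, and the plan does not say how reactions are combined across them. A paired method does not settle that, so it must be stated as well.

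**Conclusion.** For side-level proportions the Analytical Plan is wrong as written: it names an independent-samples test for within-patient data. For continuous outcomes it is unspecified, not wrong. The mismatch follows from the text alone and needs no assumption; it should be corrected, but it does not threaten the trial with false positives.

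The size of the gain depends on correlations that the documents do not give. For continuous side-level outcomes, a moderate correlation of 0.3 to 0.5 is worth roughly 10 to 25 points of power at 0.8 SD. If the sides are uncorrelated, pairing costs about 3 points. For proportions the gain is an estimate and interval that respect the design; that interval may be narrower or wider than the independent-samples one, depending on the pairing.

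**What to change.** Replace the comparison sentence in the Analytical Plan with the following:

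- RECELL-versus-placebo comparisons of side-level outcomes are within-patient.
- Any skin reaction per side, over a stated set of visits: the main result is the paired risk difference with a Tango score 95% interval. Exact McNemar replaces Fisher.
- Number of reactions per side: the mean within-patient difference, with an exact Wilcoxon signed-rank test named in advance. A paired t interval on counts is supportive only.
- Continuous side-level outcomes: paired t-test.
- A non-significant result is not evidence of safety; conclusions rest on the estimate and interval.

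**Cost.** Wording only. Comparing treated area with placebo already requires recording by side, and no extra patients, visits or measurements are needed.

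**Downsides to accept openly.**
- The exact paired tests need at least 6 patients whose sides differ. At assumed mean counts of 0.2 v 0.4 and correlation about 0.135, fewer than 6 differ in 89% of trials. The Tango interval remains available even with no discordant patient (-0.28 to 0.28).
- The interval and the test can disagree: with 5 v 0 discordant the Tango interval is 0.08 to 0.76 but McNemar p is 0.0625. The plan should therefore say that the estimate and interval come first.
- The exact signed-rank reference set of 2^10 = 1,024 sign patterns assumes that each patient's side was assigned independently. The protocol says only that a team member will "create the list of subject ID numbers with subject ID number randomly assigned to either left perioral or right perioral treatment group". A list balanced 5:5 has 252 allocations, so the method used should be recorded.
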